7.3. Blinding

This study has both single-blind (patient and caregiver) and double-blind (patient, caregiver, and investigator) phases.

To preserve the blinding of the study, a minimum number of sponsor personnel will see the randomization table and treatment assignments before the study is complete.

Emergency unblinding for AEs may be performed through the IWRS, which may supplement or take the place of emergency codes generated by a computer drug-labeling system. This option may be used ONLY if the patient's well-being requires knowledge of the patient's treatment assignment. All calls resulting in an unblinding event are recorded and reported using the IWRS.

If an investigator, site personnel performing assessments, caregiver, or patient is unblinded, the patient must be discontinued from the study. In cases where there are ethical reasons to retain the patient in the study, the investigator must obtain specific approval from the sponsor medical representative for the patient to continue in the study.

In case of an emergency, the investigator has the sole responsibility for determining if unblinding of a patient's treatment assignment is warranted for medical management of the event. The patient's safety must always be the first consideration in making such a determination. If a patient's treatment assignment is unblinded, the sponsor must be notified immediately. If the investigator decides that unblinding is warranted, it is the responsibility of the investigator to promptly document the decision and rationale and notify the sponsor as soon as possible.

7.4. Dosage Modification

Not applicable.

7.5. Preparation/Handling/Storage/Accountability

The GLWL-01 capsules are supplied in high-density polyethylene bottles. All GLWL-01 drug products will be stored in a secure and locked area with strictly limited access and monitored for temperature, and allocated and dispensed by appropriately trained personnel. Study drugs will be stored between 15°C and 30°C.

The investigator or his/her designee is responsible for the following:

- confirming appropriate temperature conditions have been maintained during transit for all study drugs received and any discrepancies are reported and resolved before use of the study drug.
- ensuring that only participants enrolled in the study may receive study drug and only authorized site staff may supply or administer study drug. All study drugs must be stored in a secure, environmentally controlled, and monitored (manual or automated) area in accordance with the labeled storage conditions with access limited to the investigator and authorized site staff.
- the investigator, institution, or the head of the medical institution (where applicable) is responsible for study drug accountability, reconciliation, and record maintenance (such as receipt, reconciliation, and final disposition records).

7.6. Treatment Compliance

Patient compliance with study drug will be assessed at the end of each treatment period. Compliance will be assessed by counting returned capsules. The patient will be considered significantly noncompliant if he or she takes <80% or >120% of dispensed capsules. Deviations from the prescribed dosage regimen should be recorded in the electronic data capture (EDC).

7.7. Concomitant Therapy

Patients may not take any medication (including over-the-counter products), herbal products, or vitamin supplements, which are CYP3A and/or P-gp inhibitors for 14 days prior to dosing and throughout the study. In cases that require the use of such medication for the treatment of an AE or comorbidity, GLWL-01 dosing must be terminated before the CYP3A inhibitor can be started.

Medications that prolong the QT/QTc interval are allowed provided the patient has been on a stable dose of said medication for at least 3 months and has a QTc < 450 msec at Visit 1 and Visit 3. A list of medications with a potential for QTc prolongation will be provided separately to the investigators.

If the need for the initiation of other medication arises during the study, the investigator must consult with sponsor medical representative and such medication change must be reported in the EDC.

All medications taken by patients during the course of the study will be recorded. Concomitant medications will be listed by treatment and coded using the most current World Health Organization drug dictionary.

7.8. Treatment after the End of the Study

Not applicable.

8. Discontinuation Criteria

Patient participation in the study may be discontinued for any of the following reasons:

- Enrollment in any other clinical study involving any study drug or enrollment in any other type of medical research judged not to be scientifically or medically compatible with this study.
- **Investigator's decision:** the investigator decides that the patient should be discontinued from the study.
- **Patient's/caregiver's decision:** the patient or caregiver requests to be discontinued from the study.
- **Sponsor's decision:** GLWL stops the study or stops the patient's participation in the study for medical, safety, regulatory, or other reasons consistent with applicable laws, regulations, and GCP.
- **Adverse event:** any SAE or a significant change in a laboratory value occurs that merits the study drug being discontinued and necessitates appropriate measures being taken. In this case, the sponsor is to be notified immediately.
- **Hepatic event or liver test abnormality:** Patients who are discontinued from using study drug due to a hepatic event or liver test abnormality should have additional hepatic safety data collected via electronic data entry.

Discontinuation of the study drug for abnormal liver test results **should be** considered by the investigator when a patient meets 1 of the following conditions after consultation with the sponsor medical representative:

- ALT or AST >5X ULN
- ALT or AST >3X ULN along with 1 of the following criteria:
 - sustained for more than 2 weeks or
 - total bilirubin level (TBL) >2X ULN or
 - prothrombin time >1.5X ULN or
 - the appearance of fatigue, nausea, vomiting, right upper-quadrant pain or tenderness, fever, rash, and/or eosinophilia (>5%)
- ALP >3X ULN
- ALP >2.5X ULN and TBL >2X ULN
- ALP >2.5X ULN with the appearance of fatigue, nausea, vomiting, right upper-quadrant pain or tenderness, fever, rash, and/or eosinophilia (>5%)
- Marked prolongation of the QT/QTc interval >500 ms or >60 ms over baseline, judged medically significant following repeat ECG after 5 minutes of rest from the initial ECG.
- A clinically significant systemic hypersensitive reaction occurs following administration of the study drug (e.g., study drug-related symptomatic bronchospasm, allergy-related edema/angioedema, or hypotension), that requires parenteral medication, does not respond to symptomatic medication, or result in clinical sequelae or an anaphylactic reaction.
- An elevated troponin I level (greater than 0.04 ng/mL); the patient must be referred for further evaluation.

- Patient has stopped eating or drinking for more than 24 hours.
- Requirement of prohibited concomitant medication.
- Patient failure to comply with protocol requirements or study-related procedures.
- Termination of the study by the sponsor or regulatory authorities.

The clinical report will include reason(s) for patient withdrawals as well as details relevant to the patient withdrawal.

Patient discontinuing from the study prematurely for any reason should complete AE and other follow-up procedures per Section 2 (Schedule of Activities), Section 9.2 (Adverse Events), and Section 9.4 (Safety) of this protocol.

A patient will be considered lost to follow-up if he or she repeatedly fails to return for scheduled visits and is unable to be contacted by the study site. Site personnel are expected to make diligent attempts to contact patients who fail to return for a scheduled visit or were otherwise unable to be followed up by the site.

9. Study Assessments and Procedures

Section 2 lists the Schedule of Activities, with the study procedures and their timing (including tolerance limits for timing).

[Appendix 2](#) lists the laboratory tests that will be performed for this study.

[Appendix 5](#) provides a summary of the maximum number and volume of invasive samples, for all sampling, during the study.

Unless otherwise stated in the subsections below, all samples collected for specified laboratory tests will be destroyed within 60 days of receipt of confirmed test results. Certain samples may be retained for a longer period, if necessary, to comply with applicable laws, regulations, or laboratory certification standards.

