Period	Screening ^a	Treatment Period 1				Washout (28 days)	Treatment Period 2			Follow-up	ET ^c	
Phase		Single-blind Placebo Lead-in Phase (14 days)	Double-blind Treatment Phase (28 days) ^b				Single-blind Placebo Lead-in (14 days)	Double-blind Treatment Phase (28 days) ^b				
Visit No/ Type Procedure	V1	V2 ^e Phone	V3 ^d	V4	V5	V6 ^e Phone	V7 ^e Phone	V8	V9	V10	V11	
Day	-28 to -3	0 (±3)	14 (±2)	21 (±2)	42 (±2)	56 (±2)	70 (±2)	84 (±2)	91 (±2)	112 (±2)	126 (±3)	
12-lead ECG ^k	X		X	X	X			X	X	X	X	X
12-lead ECG 2 hours post-dose ^k			X					X				
Serum pregnancy test ^l	X									X		X
Urine pregnancy test ^l			X					X				
Clinical chemistry and hematology ^h	X		X	X	X			X	X	X		X
Troponin			X	X	X			X	X	X		
Lipid panel			X		X			X		X		X
AG and UAG ^m			X		X			X		X		X
Plasma sample collection for PK analysis ⁿ			X		X							X
C-SSRS	X	X	X	X	X	X	X	X	X	X	X	X
Adverse events	X	X	X	X	X	X	X	X	X	X	X	X

Abbreviations: AE = adverse event; AG = acylated-ghrelin; BMI = body mass index; CGIC = Caregiver Global Impression of Change; C-SSRS = Columbia–Suicide Severity Rating Scale; ECG = electrocardiogram; EDC = electronic data capture; ET = early termination; HQ-CT = Hyperphagia Questionnaire for Clinical Trials; HBsAg = hepatitis B surface antigen; HCAB = hepatitis C antibody; HIV = human immunodeficiency virus; PK = pharmacokinetic; UAG = unacylated-ghrelin; V = Visit.

^a Screening visit must occur between -28 days to -3 days of V2.

^b Double-blind Treatment Phase must not exceed 28 days and patients must not take the study drug beyond 28 days. For example, if the V3 occurs on Day 14, then corresponding V5 would occur on Day 42. Similarly, if V3 occurs on Day 15 (Day 14 +1), then corresponding V5 would occur on Day 43 (Day 42 +1).

^c The primary reason for early termination of the patient will be entered in EDC and recorded in the patient's source documents. The patient will attend an early termination visit as soon as possible after participation ceases.

^d Confirm that the patient has met all inclusion/exclusion criteria. Patients will only be dosed after the investigator has completed the appropriate protocol assessments and determined that it is acceptable to dose the patient.

^e Patients/caregivers will receive phone calls from the site; no visit required. Both patient and caregiver should be on the phone in order for the site to conduct AE assessments and the C-SSRS.

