- n On Day 14 and Day 42, a total of 7 PK samples each day will be taken at the following times: pre-dose, and 0.5, 1, 2, 4, 6, and between 8 and 12 hours postdose. Times of sampling are intended as a guide and can be modified to accommodate clinical procedures. Actual time of sample must be collected, as well as date and time of dosing on the day of PK sample collection. For patients who discontinue early, a sample should be obtained at the ET visit.

3. Introduction

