5.1. Overall Design

This is a multicenter, double-blind, randomized, placebo-controlled, crossover study to evaluate the efficacy of GLWL-01 in patients with PWS. The study consists of 5 periods, including 2 active treatment periods, as depicted below:

Abbreviations: P = phone visit; PK = pharmacokinetic sample

Note: Placebo lead-in phases will be single-blinded (patient/caregiver) and treatment phases will be double-blinded (investigator and patient/caregiver)

Figure GLWL-PWS.1. Illustration of study design for Clinical Protocol GLWL-PWS.

The Screening Period allows for evaluation of inclusion/exclusion criteria. Treatment Period 1 consists of 2 phases: a 14-day single-blind (patient/caregiver) placebo lead-in phase followed by a 28-day double-blind treatment phase. At the conclusion of the single-blind placebo lead-in phase, eligible patients will be randomly assigned (in 1:1 ratio) to 1 of 2 treatment sequences: GLWL-01/placebo or placebo/GLWL-01 (Treatment Period 1 double-blind treatment phase/Treatment Period 2 double-blind treatment phase). Following Treatment Period 1, there will be a 28-day Washout Period. Treatment Period 2 also consists of 2 phases: a 14-day single-blind (patient/caregiver) placebo lead-in followed by a 28-day double-blind treatment phase. Following Treatment Period 2, there will be a 14-day Follow-up Period (see Figure GLWL-PWS.1).

Patients and caregivers will be required to visit the site on 8 occasions at Visits 1, 3, 4, 5, 8, 9, 10, and 11; Patients and caregivers will be required to participate in phone calls with the site at Visits 2, 6, and 7.

Study governance considerations are described in detail in [Appendix 3](#).

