6.3. Lifestyle Restrictions

Consumption of foods and beverages containing the following substances will be limited or prohibited as indicated:

- xanthine/caffeine: throughout the study, patients are required to maintain their regular intake of caffeinated beverages for the duration of the study
- Alcohol: an average weekly alcohol intake should not exceed 21 units per week (males \leq 65 years of age) and 14 units per week (females and males $>$ 65 years of age).
- Grapefruit/Seville orange: 14 days before first dosing and throughout the study.

Following the morning dose on Day 14 and Day 42, and on Day 84 and Day 112, patients will remain ambulatory or seated upright for the first 4 hours, except when they are supine or semi-reclined for study procedures.

Patients will be instructed to refrain from strenuous physical activity which could cause muscle aches or injury, including contact sports at any time from Visit 1 until completion of the study

participation. Patients should otherwise minimize changes in their activity levels during study participation.

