7.2.1. Timing of Dose Administration

The doses should be administered at approximately the same times on each day.

The study drug will be administered at the site on Days 14 and 42 (Treatment Period 1) only.

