Appendix 2. Clinical Laboratory Tests

Hematology^{a,b}		Clinical Chemistry^a
Hemoglobin		Serum Concentrations of:
Hematocrit		Sodium
Erythrocyte count (red blood cell [RBC])		Potassium
Mean cell volume		Bicarbonate
Mean cell hemoglobin concentration		Chloride
Leukocytes (white blood cell [WBC])		Calcium
Cell morphology		Phosphorus
Absolute/relative/% counts of		Magnesium
Neutrophils		Glucose (fasting)
Lymphocytes		Blood urea nitrogen (BUN)
Monocytes		Total cholesterol
Eosinophils		Total protein
Basophils		Albumin
Platelets		Total bilirubin
		Creatinine
		Estimated glomerular filtration rate (eGFR) ^d
Urinalysis^a		
Specific gravity		Alkaline phosphatase (ALP)
pH		Aspartate aminotransferase (AST)
Protein		Alanine aminotransferase (ALT)
Glucose		Gamma-glutamyl transferase (GGT)
Ketones		
Bilirubin		Tropomin I
Urobilinogen		
Blood		Additional tests
Nitrite		High-density lipoprotein cholesterol (HDL-c)
Creatinine		Triglycerides (TG)
Ethanol testing ^{b,c}		Calculated low-density lipoprotein cholesterol (LDL-c)
Urine drug screen ^{b,c}		
Hepatitis B surface antigen ^b		
Hepatitis C antibody ^b		
Human immunodeficiency virus (HIV) ^b		
Pregnancy test (serum, in females only)		
Serum follicle-stimulating hormone (FSH; in postmenopausal females only)		
Thyroid-stimulating hormone		

^a Results will be reported and/or validated by the Central Laboratory at the time of initial testing. If urinalysis is positive for protein, blood, nitrite and/or leukocyte esterase, a microscopic examination (for RBCs, WBCs, bacteria, casts, and epithelial cells) will be performed.

^b Performed at screening only.

^c Urine drug screen and ethanol level may be repeated as needed.

^d eGFR will be calculated using the Chronic Kidney Disease Epidemiology Collaboration (CKD-EPI) equation (utilizing enzymatic creatinine).

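### Troponin I above 0.04 ng/mL is a listed reason to stop, yet there is no troponin entry limit and the first draw falls on the day of randomisation and first double-blind dose

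*Protocol*

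**What the plan says.** **Stopping rule.** Protocol Section 8 opens with "Patient participation in the study may be discontinued for any of the following reasons", and one of the listed reasons is "An elevated troponin I level (greater than 0.04 ng/mL); the patient must be referred for further evaluation". Referral is compulsory; discontinuation is permitted.

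**Entry rules.** Sections 6.1 and 6.2 contain no troponin criterion. Exclusion 14 covers laboratory abnormalities by investigator judgement and gives numeric limits only for AST, ALT, GGT and ALP.

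**Timing of the draws.** The Troponin row of the Schedule of Activities is marked at Visits 3, 4, 5, 8, 9 and 10, and not at Visit 1.

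**What else happens at Visit 3.** Section 5.1: "At the conclusion of the single-blind placebo lead-in phase, eligible patients will be randomly assigned". Section 7.2.1: "The study drug will be administered at the site on Days 14 and 42 (Treatment Period 1) only". SAP 2.3 places the first double-blind dose of Period 1 on Study Day 14.

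**Dosing check.** Schedule footnote d, attached to Visit 3: "Patients will only be dosed after the investigator has completed the appropriate protocol assessments and determined that it is acceptable to dose the patient".

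**Who reads the sample.** Appendix 2 lists troponin I in the clinical chemistry column, and its footnote a says "Results will be reported and/or validated by the Central Laboratory at the time of initial testing". No turnaround time is given.

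**The concern.** A safety limit that can end participation is normally checked before a patient is exposed. Here the first look at troponin shares a visit with randomisation and the first double-blind dose, and the result may come back after both. A patient who would have failed a simple screen, or been sent for a cardiac work-up first, may instead be counted as randomised, take double-blind study drug with an unexplained raised value, and then become a candidate for discontinuation.

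The main stake is patient safety. There is also a data consequence. A patient discontinued in Period 1 has no Period 2 baseline, so the baseline-difference covariate in the primary model (SAP 6.1) cannot be formed for that patient. How often this would happen cannot be read from the documents.

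**Working it through.** The plan gives no figure to reproduce, so this is mainly a comparison of sections.

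**1. Do the draw, randomisation and first dose coincide?** Troponin starts at Visit 3, nominal Day 14. Randomisation is at the end of the 14-day lead-in, which is the same visit. The first double-blind dose is on Study Day 14 (SAP 2.3), on site (Section 7.2.1). Section 6.3 treats it as a morning dose: "Following the morning dose on Day 14 and Day 42, and on Day 84 and Day 112". Footnote n then schedules PK samples that day at "pre-dose, and 0.5, 1, 2, 4, 6, and between 8 and 12 hours postdose". All three events fall on one day, with the dose early in it.

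**2. Must the result be in hand before the dose?** Footnote d asks for completed assessments and a judgement that dosing is acceptable. It does not name troponin or require its result. Exclusion 14 can act only on a value that is known. The sample goes through a central laboratory and no same-day result is specified. So no rule requires it.

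**3. Could a Visit 1 draw be read in?** Chemistry is drawn at Visit 1 and Appendix 2 lists troponin I with chemistry. But the separate Troponin row has no Visit 1 mark, and Appendix 5 puts troponin under on-study chemistry, apart from the screening tests. Even with a Visit 1 draw, no entry limit would apply to it.

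**4. How are comparable safety markers handled?**

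| Marker | Entry limit (6.2) | Stopping limit (8) | First scheduled measurement |
|---|---|---|---|
| Liver enzymes | >3X ULN | e.g. ALT or AST >5X ULN | Visit 1 |
| QT/QTc | QTcF >450 (men) or >470 msec (women) | >500 ms, or >60 ms over baseline | Visit 1 |
| Troponin I | none | >0.04 ng/mL | Visit 3 |

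Exclusion 23c also requires QTc below 450 msec at both Visit 1 and Visit 3 for patients on QT-prolonging drugs. Gating entry on a screening value is therefore already this protocol's practice.

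**5. Would a Visit 1 result arrive in time?** Visit 1 is 3 to 28 days before Visit 2, and Visit 3 is nominally 14 days after Visit 2.
- Nominal age of a Visit 1 sample at Visit 3: 3 + 14 = 17 to 28 + 14 = 42 days.
- With Visit 2 at Day 0 ±3 and Visit 3 at Day 14 ±2, the gap between them is 14 − 5 = 9 to 14 + 5 = 19 days. The age is then 3 + 9 = 12 to 28 + 19 = 47 days.

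The result should be available, assuming a turnaround shorter than 12 days. A sample up to 47 days old can show only elevations that persist.

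**6. Scale, for illustration only.** The share p of patients already above 0.04 ng/mL at Visit 3 is not in the documents. If p is assumed, the chance of at least one such patient among N is 1 − (1 − p)^N:

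| Assumed p | N = 34 (planned) | N = 19 (anticipated, SAP 2.9) |
|---|---|---|
| 0.5% | 16% | 9% |
| 1% | 29% | 17% |
| 2% | 50% | 32% |
| 5% | 83% | 62% |

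The spread shows that the frequency cannot be settled from the documents.

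**The case against.** The strongest defence is that the plan already has several layers of protection. Exclusions 14, 17, 18 and 30 let an investigator keep out patients with worrying laboratory findings, cardiovascular illness, an abnormal ECG or general unsuitability. Entry criteria are reviewed again at Visit 3, and footnote d puts a judgement before the first dose. Section 9.2 requires investigators to document their review of every laboratory safety report. The troponin visits were added at FDA's request (Appendix 7) as on-study monitoring, and not every stopping reason needs a matching entry limit. All of this lowers the risk. None of it supplies a troponin value before exposure.

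The other side is also right to resist several stronger readings that a reader might draw:

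- **That withdrawal is automatic.** Section 8 is permissive; only referral is compulsory.
- **That an elevation could never be separated from a drug effect.** Footnote d and the baseline definitions in SAP 2.3 and 7.3 imply a pre-dose Visit 3 sample, and the post-dose ECG has its own labelled row while troponin has none. A pre-dose sample would show that the elevation came first. What is missing is an explicit label.
- **That a countable number of doses would be taken before action.** No turnaround is stated, and nothing says that a returned result waits for the next visit.
- **That screening would remove most such cases.** The documents contain no data on how long elevations persist.
- **That a dose-hold is needed.** Section 7.4 makes no provision for dosage modification, and Section 7.1 caps each double-blind phase at 28 days. A hold without a resumption rule would shorten exposure before the Day 28 endpoint.

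**Conclusion.** The point holds as a narrow gap in design. Troponin has a stopping limit, no entry limit, and a first draw on the day of randomisation and first double-blind dose, with no requirement to see the result first. A patient with a pre-existing elevation can be randomised, exposed, and then meet a listed reason for discontinuation.

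This rests on the Troponin row being complete as printed and on the absence of a result-before-dose rule elsewhere in the documents. Its size is unknown. With 1:1 allocation, about half of any affected patients would be on placebo in Period 1. No effect on dropout, power or dose count is claimed, and the primary analysis is not called into question. It is a cheap safety improvement whose remaining benefit in this trial is limited, because SAP 2.9 says enrolment was stopped with 19 patients anticipated.

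**What to change.** 1. Add troponin I to the blood already taken at Visit 1.
2. Add an exclusion to Section 6.2: troponin I above 0.04 ng/mL at Visit 1, unless evaluated and resolved before randomisation.
3. Keep the Visit 3 draw, label it pre-dose in the Schedule, and use it as the baseline. A high value returned after dosing goes through Section 8 as it stands: referral, with possible discontinuation. No dose-hold is added.

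The other on-study draws and the stopping limit stay unchanged.

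**Cost.** Amendment wording, one assay per screened patient and a few more screen failures; Section 6.4 already allows one rescreen. Screening would miss elevations that appear between Visit 1 and Visit 3. Items 1 and 2 help only patients not yet enrolled, or a later trial that reuses this design.
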